APPENDIX A

Table of Events

Visit	Screening		Week 1		Week 2		Week 3		Week 4		Week 8 ^g		Week 12		Week 13		Week 14		Week 15		Week 16		Week 17		Week 18		Week 19		Week 20		Week 24						
	0		1	2	3	4	5	6	7	8	9	10	11	12	13	14	15	16	17	18	19	20	21	22	23	24	25	26	27	28	29	30					
Visit Window ^a			±14 days								±7 days																										
Informed consent	X																																				
Eligibility criteria review	X	X																																			
Medical history & Demographics	X																																				
Height and weight	X																																				
Urine pregnancy test ^b	X	X	X						X																												
UA dipstick (with culture as needed) ^c	X									X																											
Gynecologic Pelvic examination ^d	X									X																											
Digital rectal examination ^e	X									X																											
Randomization			X																																		
Treatment: Emsella or Sham			X	X	X	X	X	X	X																												
Blinding assessment									X																												
Pain VAS	X										X																										
Pain VAS pre/post treatment			X	X	X	X	X	X	X																												
PGI-I			X	X	X	X	X	X	X																												
PGI-S	X		X						X																												
FSFI (females), BSFI (males), BDI, OAB-q, ICSI-PI, GAD7, MPQ, PCS	X									X																											
GRA										X																											
Concomitant medications	X		X	X	X	X	X	X	X																												
Adverse event(s)			X	X	X	X	X	X	X																												
Un-blinding (Sham group is offered active treatment after un-blinding) ^f														X																							

^a Visit windows may be extended due to scheduling challenges, with the goal of completing all 8 treatment visits within a 6-week window.

^b Only women of child-bearing potential will be required to have a urine pregnancy test

^c UA and C&S may be repeated if the patient is symptomatic at any other time during visits 1-8, per clinician judgment

^d Female patients will undergo a gynecologic pelvic examination to assess levator muscle tenderness

^e Male patients will undergo a digital rectal examination to assess levator muscle tenderness

^fPatients that are originally randomized to the sham treatment will be offered active treatment after the secondary endpoint visit is completed. Those patients who wish to undergo active treatment will then follow the same schedule of events as above, for visits 1-10, except for the validation of blinding questionnaire.

^gThe primary endpoint for follow up evaluation will be 4 weeks after completion of the last treatment (week 8 of the study). The durability endpoint is 4 weeks following the primary endpoint (week 12 of the study).

APPENDIX B

Data Collection Tools

Visual Analog Scale

The VAS is a self-administered questionnaire to assess overall pain and discomfort. Subjects indicate their average pain score during treatment on a straight line from 0 (no pain) to 10 (most severe pain imaginable). Extensive research supports the validity the VAS for assessment of pain intensity [34].

Patient Global Impression of Severity

The PGI-S is a global rating of subject-reported impression of the severity of a condition using a 4-point scale. Validity of the PGI-S has been established for application in SUI, pelvic organ prolapse, and other non-urologic disease [35].

Patient Global Impression of Improvement

The PGI-I is a global rating of subject-reported impression of improvement in a specific medical condition using a 7-point scale. Validity of the PGI-I has been established for application in SUI, pelvic organ prolapse and other non-urologic disease including pain [35].

Female Sexual Functioning Index

The FSFI is a self-administered questionnaire to assess overall sexual experience that consists of 19 questions that are scored from 0 to 5. The scale contains 6 domains: desire, arousal, lubrication, orgasm, satisfaction, and pain. The FSFI total score is a weighted average of the 6 domains with each contributing a maximum of 6 points to the total (maximum score of 36) [36].

Brief Sexual Function Inventory

The BSFI is a self-administered questionnaire to assess male sexual function. It includes the following domains; sexual drive (two items), erection (three items), ejaculation (two items), perceptions of problems in each area (three items), and overall satisfaction (one item). The BSFI is scored on a 5-point scale, where the scores for each domain are computed separately from one another [37].

Beck Depression Inventory

The BDI is a 21-question multiple-choice self-report inventory, and one of the most widely used psychometric tests for measuring the severity of depression. It is composed of items relating to symptoms of depression such as hopelessness and irritability, cognitions such as guilt or feelings of being punished, as well as physical symptoms such as fatigue, weight loss, and lack of interest in sex. Subjects that score >30 at any time throughout the trial may be referred for psychological evaluation but may continue study participation.

Overactive Bladder Questionnaire-Short Form (OAB-Q)

Since both overactive bladder and IC/BPS share urinary urgency and frequency symptoms, this validated measure will evaluate additional aspects of symptoms associated with IC/BPS. The OAB-Q consists of symptom severity and health related quality of life scales (HRQOL) [38]. Statistically significant correlations have been found between the OAB-q SF scales and other patient reported outcomes instruments. For example, higher levels of depressive symptoms as

measured by the CES-D were linearly related to higher levels of Symptom Bother (r 0.31, $P < 0.0001$) and lower levels of HRQL on the OAB-q SF (r 0.35, $P < 0.0001$). Both the Symptom Bother and HRQL scales easily differentiated between Control without overactive bladder (OAB), Continent patients with OAB and incontinent OAB patients ($P < 0.0001$). These results provide evidence that the Symptom Bother and HRQL short-forms developed in this study are valid and can be used in a clinical or research context to differentiate OAB patients from normal, healthy individuals.

Interstitial Cystitis Symptom Index and Problem Index (ICSI-PI)

The IC symptom and problem indices measure urinary and pain symptoms and assess how problematic symptoms are for patients with IC/PBS. Psychometric performance of both instruments is good, with the symptom index demonstrating excellent ability to discriminate characteristics between patients and controls.

Generalized Anxiety Disorder Questionnaire (GAD-7)

The GAD-7 questionnaire is a 7-item validated scale to assess generalized anxiety disorder. On the GAD-7, patients are grouped by GAD score 0-7 and 8+ which suggests no anxiety disorder and probable anxiety disorder, respectively.

McGill Pain Questionnaire (MPQ)

The McGill Pain Questionnaire can be used to evaluate a person experiencing significant pain. It can be used to monitor the pain over time and to determine the effectiveness of any intervention [39]. It was developed at McGill University in Montreal Canada and is widely used in pain research.

Pain Catastrophizing Scale (PCS)

Pain catastrophizing is the tendency to describe a pain experience in more exaggerated terms than the average person, to ruminate on it more (e.g., "I kept thinking 'this is terrible'"), and/or to feel more helpless about the experience ("I thought it was never going to get better"). People who report a large number of such thoughts during a pain experience are more likely to rate the pain as more intense than those who report fewer such thoughts. The PCS is a validated measure of rumination, magnification, and helplessness related to pain. The PCS has been shown to have adequate to excellent internal consistency (coefficient alphas: total PCS = .87, rumination = .87, magnification = .66, and helplessness = .78) [40].

Global Response Assessments (GRA) for Pain and QOL

GRA evaluate the patients' perceptions of overall improvement in symptoms on a 7-point scale (markedly worse, to markedly improved). GRAs have been widely used as primary endpoints in IC/BPS trials [41], and have been correlated with voiding diary records [42].

Validation of Blinding Questionnaire

The validation of blinding questionnaire will be given to evaluate the patients' perception of stimulation received. Patients will be asked if they received active stimulation or sham stimulation. Patients will also be asked how confident they are in their answer, this is measured on a scale from 1-5 (1 is not confident at all and 5 is completely confident).

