Electromagnetic stimulation of the pelvic floor with the Emsella device is a FDA 510(k) approved therapy whereby a coil generates pulsed electromagnetic fields that penetrate deep into the pelvic floor muscles inducing stimulation and providing rehabilitation of weak pelvic muscles. It was first described as a conservative treatment for stress urinary incontinence (SUI) in 1999 and demonstrated encouraging results [28]. The Emsella Chair is a novel high intensity focused electromagnetic (HIFEM) technology, currently used for the treatment of SUI, in addition to other pelvic floor related disorders. The program phases consist of an intense awakening of the deconditioned pelvic floor muscles (cat), stimulation, and relaxation. The repetition of the phases and focused electromagnetic energy delivery leads to pelvic floor stimulation, adaptation, and remodeling. Alternative settings of pulse strength and frequency could theoretically be used to

stimulate the PFM without inducing muscular contraction. This could induce fatigue in muscle groups, leading to muscle relaxation & reduced hypertonic pelvic floor dysfunction in a manner similar manner to PFPT.

This technology is typically not covered by insurance, is minimally invasive, and safe, but has limited data available. Currently, there is no data available evaluating efficacy of this technology for CPP. The purpose of this study is to compare the Emsella Chair to sham and to determine whether electromagnetic technology is effective in the treatment of CPP.

OBJECTIVES AND ENDPOINTS

Primary Objective - Efficacy

The primary objective of this study is to compare the efficacy of Emsella Chair to sham by evaluating the change in subject-reported pain and discomfort as measured by the Visual Analog Scale (VAS). Mean change in VAS from baseline to end of treatment will be compared between the Emsella Chair group and the sham group.

Hypothesis: Subjects in the Emsella Chair group will show a greater decrease in pain, as measured by VAS, compared to subjects in the sham group.

Secondary Objectives - Efficacy

The secondary efficacy objectives in this study are to compare the Emsella Chair versus sham in relation to several different domains (pain, urinary symptoms, sexual function, quality of life) using validated questionnaires.

- Change in subject-reported impression of CPP severity as measured by the Patient Global Impression of Severity scale (PGI-S)

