- Change in subject-reported impression of CPP improvement as measured by the Patient Global Impression of Improvement scale (PGI-I)
- Change in subject-reported pelvic floor tenderness to palpation during 4 quadrant pelvic examination as measured by VAS
- Change in subject-reported sexual function as measured by the Female Sexual Function Index questionnaire (FSFI) for female subjects
- Change in subject-reported sexual function as measured by the Brief Sexual Function Inventory questionnaire (BSFI) for male subjects
- Change in subject-reported depression severity as measured by the Beck Depression Inventory (BDI)
- Change in subject-reported bother related to overactive bladder symptoms as measured by the Overactive Bladder Questionnaire-Short Form (OAB-Q)
- Change in subject-reported urinary and pain symptoms, as well as bother, as measured by the Interstitial Cystitis Symptom Index and Problem Index (ICSI-PI)

- Change in subject-reported anxiety symptoms as measured by the Generalized Anxiety Disorder Questionnaire (GAD-7)
- Change in subject-reported pain as measured by the McGill Pain Questionnaire (MPQ)
- Change in subject-reported rumination, magnification, and helplessness related to pain as measured by the Pain Catastrophizing Scale (PCS)
- Patient-Reported perception of overall improvement in symptoms as measured by Global Response Assessments (GRA) for Pain and Quality of Life

Secondary Objective – Durability

The secondary durability objective for this study is to determine whether subjects in the Emsella Chair group continue to have decrease in pain, as measured by VAS, compared to the Sham group 4 weeks after the primary efficacy endpoint.

Secondary Objective - Safety

The secondary safety objectives of this study are to determine the safety and tolerability of Emsella Chair compared to sham. Safety and tolerability will be assessed in relation to the following:

- Incidence of adverse events (AEs)

Exploratory Objective

- None

Endpoints

The primary efficacy endpoint is 4 weeks after completing all treatments; week 8 of the study. Treatment durability will be assessed 4 weeks after the primary endpoint; week 12 of the study.

Safety Assessment

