Once informed consent is obtained, a study identification number will be assigned. A detailed interview will be conducted, including demographics, medical history, past surgical, gynecological and obstetric history (if applicable), and concomitant medications. Subjects will complete a baseline visual analog pain scale. Weight will be measured. Females will undergo a gynecologic pelvic examination, which includes assessment of levator muscle tenderness. For male subjects, a digital rectal examination will be performed to assess levator muscle tenderness. A dipstick urinalysis will be performed. If positive for leukocytes, a urine culture will be sent. If a subject has a confirmed symptomatic urinary tract infection

(UTI) per investigator's clinical judgment, they will be deferred from screening until treatment is completed and may resume once symptoms resolve. If the female subject is of child-bearing potential, a urine pregnancy test will be performed. If the urine pregnancy test is positive, the subject will be ineligible for study participation. Subjects will complete self-administered questionnaires (PGI-S, FSFI or BSF, BDI, OAB-q, ICSI-PI, GAD 7, MPQ, PCS). Adverse events will be assessed at each study visit including the screening visit. Screening activities may be completed at Visit 1, prior to randomization, if needed. Data collected prior to randomization will be considered baseline.

Study Visit 1: Week 1

A urine pregnancy test (if applicable) will be performed. If the urine pregnancy test is positive, the subject will be ineligible for study participation. Additionally, any screening activities that were not completed at the initial visit will be conducted. After all screening activities are completed, and it is determined that the subject meets the eligibility criteria, the subject will be enrolled in the study and randomized to one of the two intervention arms. The first treatment will be conducted at this visit.

The subject will complete VAS before and after treatment. Concomitant medications and adverse events will be reviewed and changes from the previous visit will be recorded.

If at any time a patient reports a fever, an oral temperature will be obtained. If a fever, defined as $\geq 38^{\circ}$ Celsius, is present, treatment will be delayed until the fever is resolved at a later visit.

Study Treatments: Visit 2-Visit 8

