Subjects will return 2 times per week for Emsella Chair or sham treatments for 4 consecutive weeks. Treatments will ideally be delivered at least 2 days apart from one another. Should scheduling challenges occur, the goal will be to complete all 8 treatment visits within a 6-week window. Prior to conducting the first treatment each week a urine pregnancy test (if applicable) will be performed. If the urine pregnancy test is positive, the subject will be withdrawn from the study. VAS-pain will be completed by subject pre- and post each treatment visit. Additionally, before each second weekly treatment visit, the subject will complete the PGI-I and PGI-S. At visit 8, the subject will complete a treatment blinding assessment, indicating if they believe they received active or sham treatment. Concomitant medications and adverse events will be reviewed and changes from the previous visit will be recorded.

If at any time a patient reports a fever, an oral temperature will be obtained. If a fever, defined as $\geq 38^{\circ}$ Celsius, is present, treatment will be delayed until the fever is resolved at a later visit.

Urine dipstick will not routinely be collected for analysis at the study treatment visits. However, as standard of care, if UTI symptoms are reported by the subject, urinalysis via dipstick will be performed. If positive for leukocytes, a urine culture will be sent, and the subject will be treated appropriately. Subjects will be allowed to continue study treatments if they are being treated for a UTI, unless they have a fever, defined as temperature $\geq 38^{\circ}$ Celsius.

Follow-up Visits

Visit 9, Week 8, Primary Endpoint

Approximately 4 weeks after finishing treatment, the subject will return to the study site for a clinic visit. A dipstick urinalysis will be performed. If positive for leukocytes, a urine culture will be sent. If the subject has a confirmed symptomatic UTI, per investigator's clinical judgment, the remaining activities for this visit will be postponed until treatment is completed and symptoms have resolved. The subject will complete the VAS, PGI-I, PGI-S, FSFI (females only) or BSFI (males only), BDI, OAB-q, ICSI-PI, GAD7, MPQ, PCS, and GRA. Concomitant medications and adverse events will be reviewed and changes from the previous visit will be recorded. For female subjects, a gynecologic (female) or digital rectal (male) exam will be completed with palpation of levator muscles for assessment of tenderness.

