- Temporary joint or tendon pain
- Local skin redness
- Temporary increase of local circulation or blood flow
- Increased sensitivity during intercourse
- Heavier bleeding and/or cramping if treatments are administered during menstruation

Possible Risk of Breach of Privacy and Confidentiality

- There is a rare risk of breach of privacy and data confidentiality (release of information which personally identifies the subject). Confidentiality procedures will be strictly adhered to when transferring, managing, and analyzing study data. The subject will be assigned a unique study identification number and research information will be stored in a locked, secure cabinet in the Urology Research suite with access limited to authorized research personnel. Study data will be maintained in a password protected file on a shared network that can only be accessed by Urology research personnel.

Possible Benefits

- Improvement of chronic pelvic pain symptoms
- Improvement in quality of life

ELIGIBILITY CRITERIA

Inclusion Criteria

Each subject must meet all the following criteria to be enrolled in this study:

1. Able to read, understand, and provide written, dated, informed consent prior to screening, and be likely to comply with study protocol, including independently complete study questionnaires and communicate with study personnel about AEs and other clinically important information.
2. Females and males, 18 to 80 years of age, at screening
3. Self-reported CPP defined as pelvic pain that is non-cyclical and of at least 6 months duration and refractory to other treatments
4. Self-reported pelvic pain score ≥ 4 on VAS
5. Subject agrees not to start any new treatment for CPP (medication or otherwise) during the treatment and follow-up periods.
6. Subject agrees to maintain a stable dose all current medications throughout the treatment and follow-up period

For Females Only:

7. If of child-bearing age and female, agree to practice approved birth-control methods (oral contraceptives, condom barrier, injection, diaphragm or cervical cap, vaginal contraceptive ring, IUD, implantable contraceptive, surgical sterilization (bilateral tubal ligation), vasectomized partner(s))

Exclusion Criteria

A subject meeting any of the following criteria will be excluded from study participation:

1. Pelvic floor physical therapy, including muscle training and/or electrostimulation, in a clinical setting within 30 days prior to screening.

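### The only recall period given for the pain VAS, average pain during treatment, cannot apply at baseline and points to a finished period at Week 8 and Week 12

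*Combined protocol and SAP*

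**What the plan says.** Appendix B, Visual Analog Scale, describes the instrument as a measure of overall pain and discomfort and gives one instruction: "Subjects indicate their average pain score during treatment on a straight line from 0 (no pain) to 10 (most severe pain imaginable". I found no other time frame for this scale in the protocol.

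The pain VAS has five uses:

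- **Entry cut-off** (Inclusion Criteria, item 4): "Self-reported pelvic pain score ≥ 4 on VAS".
- **Baseline** (Screening: Visit 0): "Subjects will complete a baseline visual analog pain scale". Anything collected before randomization counts as baseline.
- **Around each session** (Study Visit 1 and Study Treatments: Visit 2-Visit 8): "VAS-pain will be completed by subject pre- and post each treatment visit".
- **Primary outcome** (Endpoints; Visit 9): "The primary efficacy endpoint is 4 weeks after completing all treatments; week 8 of the study".
- **Durability** (Secondary Objective – Durability; Visit 10): whether active subjects "continue to have decrease in pain, as measured by VAS, compared to the Sham group 4 weeks after the primary efficacy endpoint".

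The Table of Events in Appendix A has one row for the pain VAS and another for the pain VAS before and after treatment. Neither row carries its own wording.

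**The concern.** A change score needs the same question at both ends. Here the one documented question cannot be answered at the start, since there has been no treatment to rate, and at the end it directs the subject to a period that is over. The visit schedule fixes when the form is completed. It does not fix which days the subject is rating.

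The primary comparison is the change in this score to Week 8. The responder category (at least a 50% decrease from baseline) and the imputed Week 8 responder status are built on the same score. If the instruction is followed, the Week 8 result may describe a different period from the one the Endpoints section names, and Week 12 may repeat that period instead of showing whether benefit lasted. If subjects set the instruction aside, each chooses a window (now, today, the past week), and the choice may differ between visits. The separate SAP promised under Methods can describe what was rated, but it cannot change the question once readings have been taken.

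**Working it through.** This is a question of outcome definition, so the main check sets the instruction against each use.

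**Count of readings in the randomized period.** Screening 1, before and after eight sessions 8 × 2 = 16, Week 8 and Week 12 together 2. Total 1 + 16 + 2 = 19.

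**Two meanings of treatment.** The protocol uses the word both for the 4-week course (Endpoints; Visit 9) and for a single session of up to about 28 minutes (Methodology; Study Visit 1).

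| Reading | If treatment = the course | If treatment = one session |
|---|---|---|
| Screening / baseline (1) | nothing to rate | nothing to rate |
| Before session 1 (1) | nothing to rate | nothing to rate |
| Before sessions 2–8 (7) | course so far | at best the previous session |
| After sessions 1–8 (8) | course so far | fits |
| Week 8, primary (1) | course that ended about 4 weeks earlier | no session to rate |
| Week 12, durability (1) | same course, ended about 8 weeks earlier | no session to rate |

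Under neither meaning do baseline and Week 8 share a valid window. Under the course meaning, Weeks 8 and 12 ask about the same weeks, so a benefit lost after treatment would still be reported at both. Under the session meaning, the wording fits 8 of the 19 readings, none of which is the baseline, primary or durability reading.

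**The plan's own figure.** Sample Size Calculation: 30 per arm, SD 2.5 cm at both times, correlation 0.2, 80% power, 5% level (taken as two-sided).

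- SD of change = 2.5 × √(2 × (1 − 0.2)) = 3.162 cm.
- Detectable difference = (1.960 + 0.842) × 3.162 × √(2/30) = 2.29 cm by normal approximation, or 2.33 cm by noncentral t. The plan states 2.3 cm, so it reproduces.
- Power at 2.3 cm by noncentral t is 79%.

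**Illustration only.** Suppose the form carries the Appendix B words, subjects read treatment as the course and recall it accurately, the true Week 8 effect is 2.3 cm, and a t test on change is used. The time course is not in the documents, so a range is assumed. The measured effect is then 2.3 cm times the fraction of the final effect averaged over the 16 session readings:

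| Assumed time course | Fraction | Measured effect | Power, r = 0.2 |
|---|---|---|---|
| Full from the first session | 1.00 | 2.30 cm | 79% |
| Linear, full by session 4 | 0.75 | 1.73 cm | 55% |
| Linear over eight sessions | 0.50 | 1.15 cm | 28% |
| Linear, starting after session 4 | 0.25 | 0.58 cm | 11% |

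At r = 0.5 the linear eight-session case gives 42%, against 94% undiluted. In the opposite case, an effect averaging 2.3 cm during the course and nil at Week 8 would be significant 79% of the time, against 5% (2.5% in favour of active) if Week 8 pain were asked. The conclusion does not rest on these figures.

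**The case against.** Appendix B summarises instruments and is not shown to be the question put to subjects. It states no recall window for FSFI, BDI, OAB-q, GAD-7, MPQ or PCS either. If the VAS form carries a suitable window, the harm disappears and what remains is a description to correct. This stands, and it makes every consequence conditional on the form. It does not remove the point: the one window that is written for the primary instrument does not fit baseline or follow-up.

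The phrase may come from a post-session form and have been carried into a general description. Appendix A's two rows make that plausible, so a reader should not infer that one identical form is used at all 19 readings. But if so, the baseline, Week 8 and Week 12 readings are left with no stated window.

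A reader might take the Primary Objective, "Mean change in VAS from baseline to end of treatment will be compared between the Emsella Chair group and the sham group", as confirmation that the treatment weeks are meant to be rated. It does not support that: the sentence concerns when change is measured, not what period is recalled, and Endpoints, Methodology, Visit 9, Methods and the notes to Appendix A all place the primary endpoint or period at Week 8. That timing inconsistency is a separate point, as is the VAS for tenderness on palpation.

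A reader might also infer that the trial's power falls to 28% or 11%. The documents do not support that either. Those figures need an assumed time course, literal recall of weeks that have passed, and a t test in place of the planned ordinal regression; one of the assumed courses shows no loss at all.

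Finally, MPQ, PGI-S, PGI-I and GRA are also collected at Weeks 8 and 12. They give supporting evidence at follow-up, but they are secondary and do not replace the VAS.

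**Conclusion.** The point holds as one of outcome measurement. The documented VAS instruction is wrong as written for the readings that matter most: it cannot apply at screening and baseline, and at Weeks 8 and 12 it refers to treatment that ended about 4 and 8 weeks before. If treatment means the course, durability cannot be judged from the Week 8 and Week 12 readings. If it means a session, the primary outcome has no valid window.

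The conclusion rests on two things: that Appendix B is the only statement of a recall period, which is true of the documents, and that the form does not say something better, which cannot be checked. The documents do not allow the effect on the result to be sized. They do not support a claim of bias towards either arm, since both complete the same assessments at the same visits, nor a claim that the sample size is miscalculated. The point should be corrected because the primary endpoint depends on it and the correction is cheap.

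**What to change.** In Appendix B and on the VAS form, replace the reference to treatment with an instruction for each use:

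1. **Screening/baseline, Week 8 and Week 12:** one identical fixed window, for example average pelvic pain over the past 7 days. Seven days is one reasonable choice; what matters is that the window is the same at all three.
2. **Before and after each session:** pelvic pain right now.

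In Appendix A, note which wording belongs to each of the two pain VAS rows. If the form already carries a suitable window, leave the form alone and correct Appendix B to match it.

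If subjects have already been enrolled on the existing wording, keep the wording constant within each subject, state in the separate SAP which period was rated, and limit the Week 8 and Week 12 conclusions to that period.

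The cost is a short amendment and one sentence per use, with no new visits or procedures. The drawbacks are that staff must keep two VAS wordings apart, and that subjects assessed under different wordings could be pooled only with a caveat.
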